**8) Study Endpoints**

Primary outcome:

- Proportion of patients with vision loss to 20/40 or worse on ETDRS testing on two visits  $\leq 28$  days apart at 12 and 24 months.
- Mean time to vision loss to 20/40 or worse on ETDRS testing on two visits  $\leq 28$  days apart

Secondary Outcomes:

- Mean change in visual acuity, low luminance visual acuity and contrast sensitivity at 3, 6, 9, 12, 15, 18, 21, and 24 months from baseline
- Mean change in central macular thickness (CMT) on OCT at 3, 6, 9, 12, 15, 18, 21, and 24 months from baseline
- Mean change in retinal sensitivity assessed by microperimetry at 3, 6, 9, 12, 15, 18, 21, and 24 months from baseline
- Percentage of subjects with visual acuity loss (including low luminance visual acuity and contrast sensitivity) of  $\geq 5$  letters at 12 and 24 months
- Percentage of subjects with at least 10 and 15 letter gain or loss at 12 and 24 months
- Visual acuity area under the curve at 12 and 24 months
- Number of SML treatments received at 12 and 24 months
- Number of anti-VEGF treatments received at 12 and 24 months
- *Any safety concerns documented during the study*

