**7) Study Timelines**

- The duration of an individual subject’s participation in the study will be two years which will include at least 10 total visits at various time points including on the day of enrollment, followed by 1, 3, 6, 9, and 12, 15, 18, 21, 24 months after the day of enrollment
- The duration anticipated to enroll all study subjects is 1 year
- The estimated date for the investigators to complete this study is December 2023
- 36 eyes will be enrolled based on power calculations for 80% power assuming at least 40% of eyes monitored by observation alone will experience vision loss to 20/40 or worse, and that SML treatment will reduce that value to 15%, using a 2:1 ratio for randomization (2 treatment : 1 observation (sham)). The ETDRS study showed that among eyes with good visual acuity (20/25 or better), 40% will experience a visual acuity decrease by 5 letters or more. We assume a higher rate among eyes with 20/32 or better.

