**FIGURE 1**

TxCell 7 x 7 grid pattern (49 spots)

**PROTOCOL TITLE: Micropulse for suppression of diabetic macular edema  
“PULSE STUDY”**

9. Confirm that the patient can detect at least finger-counting vision after laser procedure.

Those in the sham treatment arm will undergo the same set up procedures as described above, however, no actual laser treatment will occur. Subjects will then return to the clinic for repeat ophthalmic exam, OCT imaging, and microperimetry at 1 month, 3 month, 6 month, 9 month, 12 month, 15 month, 18 month, 21 month and 24 month time points, which is similar in frequency as standard of care. Patients in the treatment arm are eligible for repeat SML laser at any subsequent visit if there is any decline in vision (1 or more ETDRS lines) or worsening in edema (>10% increase), at the discretion of the treating physician. If vision declines to 20/40 or worse at any study visit, patients in the treatment arm will undergo repeat treatment with SML laser, while those in the sham arm will undergo repeat sham laser.

If the patient demonstrated 20/40 or worse ETDRS visual acuity at any study visit, he or she will be required to return within 28 days for repeat ETDRS visual acuity testing, ophthalmic exam, OCT imaging, and microperimetry. If the patient demonstrated 20/40 or worse ETDRS visual acuity at this repeat visit, then the patient will have reached study endpoint and be considered treatment failure. At that visit, patients may be given any combination of intravitreal anti-VEGF injection (preferred based on DRCR.net protocol I and protocol T), focal/grid laser, repeat SML treatment, or intravitreal steroid injection, based on the discretion of the investigator. After study endpoint (visual acuity loss to 20/40 or worse), patients may be treated on a monthly, pro re nata (PRN), or "treat-and-extend" basis based on the individual investigator's preference. Patients are still required to continue with study visits, but any additional visits or treatments, although still documented, will be considered off-study.

All data will be analyzed in accordance to the “intention-to-treat” principle.

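### A primary outcome is a mean time to vision loss with no time limit, yet on the planning rates about 22 to 28 of 36 eyes have no event within the 24-month follow-up

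*Protocol*

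**What the plan says.** Protocol Section 8 lists two primary outcomes built on the same event, ETDRS acuity of 20/40 or worse confirmed at a second visit. The first is "Proportion of patients with vision loss to 20/40 or worse on ETDRS testing on two visits", and it carries time points: "days apart at 12 and 24 months". The second is "Mean time to vision loss to 20/40 or worse on ETDRS testing on two visits", and it carries none.

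Section 7 states that "participation in the study will be two years". It sizes the trial at 36 eyes, allocated two SML to one sham, "assuming at least 40% of eyes monitored by observation alone will experience vision loss to 20/40 or worse", with SML lowering that figure to 15%. It does not say by what time these rates apply.

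In Section 9, once the loss is confirmed at the repeat visit, "then the patient will have reached study endpoint and be considered treatment failure". The same section commits all analyses to intention-to-treat. Nothing in the protocol says how an eye that never fails enters the mean.

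**The concern.** A mean event time needs an event time for every eye. If follow-up stops at 24 months while most eyes are still event-free, the data do not determine that mean. Two literal readings remain:

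- **All eyes.** The part of the distribution beyond 24 months has to come from a model.
- **Failures only.** The comparison is then between subgroups selected by the outcome itself. That conflicts with the intention-to-treat commitment, and the summary hardly reacts to the planned effect, which is fewer failures.

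This outcome carries the hypothesis in Section 4 that SML delays vision loss. If it cannot be used as named, someone will have to replace a primary summary measure, possibly after seeing data.

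There is also a smaller wording point. Section 8 gives the companion proportion at 12 and 24 months, whereas Section 9 treats confirmed loss at any visit as an endpoint reached, which is a cumulative status.

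**Working it through.** **Inputs.** From Section 7: 36 eyes at 2:1, so 24 SML and 12 sham; failure rates of 40% (a minimum) and 15%; follow-up of 24 months. Assumed: constant hazards, no dropout, two-sided 5% tests. Because the rates are undated and the sham rate is a minimum, three scenarios are shown.

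**The plan's own figure.** The 36 eyes relate to the proportion outcome. The usual two-proportion formula for 40% versus 15% at 2:1, 80% power and two-sided 5% gives 36 sham eyes and 108 in total, so 36 in total does not reproduce. That is a separate matter, and nothing below depends on it.

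**Formulas.** With failure rate p by time t:

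- hazard h = −ln(1 − p)/t
- S = exp(−24h), the proportion event-free at 24 months
- unrestricted mean = 1/h
- mean among failures = 1/h − 24·S/(1 − S)
- 24-month restricted mean = (1 − S)/h

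**Base case (40% and 15% by 24 months).**

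- Event-free eyes: 12 × 0.60 + 24 × 0.85 = 7.2 + 20.4 = 27.6 of 36 (77%). Failures: 4.8 + 3.6 = 8.4.
- h = 0.0213 (sham) and 0.0068 (SML); hazard ratio ln(0.85)/ln(0.60) = 0.32.
- Unrestricted mean: 47.0 versus 147.7 months.
- Failures only: 47.0 − 24 × 0.60/0.40 = 11.0; 147.7 − 24 × 0.85/0.15 = 11.7 months.
- Restricted mean: 0.40 × 47.0 = 18.8; 0.15 × 147.7 = 22.2 months.

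**All scenarios (sham versus SML, months).**

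| Scenario | Event-free of 36 | Unrestricted mean | Failures only | Restricted mean |
|---|---|---|---|---|
| 40%/15% by 24 months | 27.6 | 47.0 vs 147.7 | 11.0 vs 11.7 | 18.8 vs 22.2 |
| 60%/15% by 24 months | 4.8 + 20.4 = 25.2 | 26.2 vs 147.7 | 10.2 vs 11.7 | 15.7 vs 22.2 |
| 40%/15% by 12 months (S = 0.36 and 0.7225 at 24) | 4.3 + 17.3 = 21.7 | 23.5 vs 73.8 | 10.0 vs 11.4 | 15.0 vs 20.5 |

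**Dependence on the tail.** The base-case 24-month rates were kept and the constant hazard replaced by a Weibull with shape 1.5, 1 or 0.7. The sham mean is then 34, 47 or 79 months and the SML mean 73, 148 or 407 months. All of these pass through the same event-free proportions at 24 months.

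**Power by simulation.** 6,000 trials, 12 sham and 24 SML eyes, events recorded at the protocol visits:

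| Scenario | Log-rank | Restricted mean | t-test among failures |
|---|---|---|---|
| 40%/15% by 24 months | 42% | 25% | 5% |
| 60%/15% by 24 months | 83% | 66% | 7% |
| 40%/15% by 12 months | 60% | 47% | 7% |

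In the base case one arm has fewer than two failures in 12% of trials. Where both arms have at least two, the SML failures-only mean is the shorter one in 43%. With ten times as many eyes (1,500 trials) the t-test among failures still has only 7% power, while log-rank reaches 100%. The weakness therefore lies in the summary measure as well as in the sample size.

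**The case against.** The strongest reply is that this is a gap a SAP may fill. Section 8 is a list of endpoints, Section 11 refers to standard statistical methods, and censoring rules, Kaplan-Meier curves and a restriction time often sit in a SAP. On that view the two-year participation supplies the horizon, a mean event-free time within 24 months is an available reading, and nobody has proposed averaging the failures alone.

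Part of this stands. The protocol does not use the word unrestricted, and the failures-only analysis is one possible reading, not a stated plan. But the protocol itself names the summary measure of a primary outcome, and names it without the horizon that it gives to the proportion directly above. A SAP that used Kaplan-Meier or a restricted mean would be replacing that measure. The general reference to standard methods does not change it.

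The range can also be challenged. Reading a 60% sham rate and the 15% SML rate both as 12-month rates leaves 12 × 0.16 + 24 × 0.7225 = 19.3 eyes event-free. Section 9 places the two eyes of a bilateral patient in opposite arms, so a 24/12 split is not assured; at 18/18 the base case gives 26.1 and the 12-month case 19.5. These points widen the range but do not reverse it. More than half of all eyes, and about 72% or more of SML eyes, remain event-free in each case.

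Finally, SML might postpone the same number of failures, and that could move the failures-only mean. Section 7 plans fewer failures instead.

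**Conclusion.** The concern holds and should be fixed before data are seen. As named, the second primary outcome yields either a model-dependent extrapolation or a mean over a small outcome-selected group (about 8 eyes in the base case, about 14 on the 12-month reading). The latter differs by 0.7 to 1.5 months between arms in the three main scenarios and has 5% to 7% power.

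The range of about 22 to 28 event-free eyes assumes constant hazards, a 24/12 split and no loss to follow-up. Its upper end reads the rates as 24-month rates and its lower end as 12-month rates. The conclusion does not depend on which reading is taken.

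The consequence is limited: the proportion on which the trial is sized can still address vision loss. The at-versus-by wording of that proportion is minor.

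**What to change.** - Restate the outcome in Section 8 as time from randomization to confirmed acuity of 20/40 or worse, with event-free eyes censored at their last visit or at 24 months.
- Analyse it by Kaplan-Meier curves and a log-rank test. Report the between-arm difference in 24-month restricted mean event-free time as the mean-time summary.
- Word the companion proportion as cumulative, by 12 and by 24 months, to agree with Section 9.

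The cost is a change of endpoint wording; the visits and data are already planned. It does not repair the low power at 36 eyes (in the base case about 42% for log-rank and 25% for the restricted mean), which needs to be dealt with separately.

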## **PROTOCOL TITLE: Micropulse for suppression of diabetic macular edema “PULSE STUDY”**

### **9) Procedures Involved**

This is a randomized, controlled clinical trial comparing subthreshold micropulse laser versus sham laser treatment for eyes with diabetic macular edema with good visual acuity of 20/32 or better. After signing written consent and enrolling in the study, patients will be randomized to receive either subthreshold micropulse laser treatment or no treatment (sham). Randomization will occur as a ratio of 2:1 and will take place during the clinic visit. A block randomization scheme will be created before the study begins to ensure appropriate treatment allocation among the two groups. At the time of randomization, only one eye will be randomized to either the treatment or observation. If both eyes meet the inclusion criteria, one eye (worse eye) will be assigned to the treatment group and the fellow eye to the sham treatment group. Subjects selected for the study will then undergo a complete ophthalmic examination, including measurements of best corrected visual acuity, low luminance visual acuity, contrast sensitivity (using ETDRS testing with a masked coordinator), intraocular pressure, slit lamp exam including documentation of lens status, and dilated funduscopy exam with standard dilating agents used at the UC Davis Eye Center. Subjects will then undergo baseline imaging with SD-OCT and fundus autofluorescence (FAF) using the Spectralis OCT+SLO instrument (Heidelberg Engineering, Heidelberg, Germany) and Optos (Optos Inc.). The Optos imaging system will only be used as a back up to the Heidelberg, as well as microperimetry testing using Nidek MP-1 instrument (Padova, Italy). Both the use of OCT, FAF, and microperimetry testing are within the standard of care for the management of DME.

For OCT and FAF, a lubricating artificial tear drop may be used on subjects with dry eyes to enhance image quality as is routinely done. Each eye will have 3-4 images acquired, which will take approximately 30-45 seconds for each eye. OCT imaging must include at least one high resolution scan across the fovea, and central macular thickness measured as determined using the OCT instrument's algorithm. FAF imaging must include the entire macular region through which the micropulse laser treatment will be applied.

For microperimetry, a built-in fundus camera is used to focus on the patient's retina and fundus tracking ensures fixation stability. As the patient perceives the stimulus, they press a trigger which is then recorded similar to other widely used perimetry tests (Humphrey visual field test). Testing will take approximately 3-4 minutes per eye.

Qualified ophthalmic personnel (physicians, certified ophthalmic technicians, and certified ophthalmic photographers) under a study personnel supervision will administer all eye drops, perform the ophthalmic exam, and capture images on the Spectralis OCT and MP-1 microperimeter.

[figure not shown]
[figure not shown]
The subjects in the treatment arm will be treated on the day of randomization by SML photocoagulation using the Iridex IQ577 laser unit with TxCell scanning laser delivery system. Treatment will involve the following steps:

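### The 2:1 block scheme is not stratified by baseline acuity, although the primary event is a fixed level one line below the entry limit; with 12 sham eyes this costs precision that is cheap to recover

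*Protocol*

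**What the plan says.** - **Allocation (protocol section 9, Procedures Involved).** Randomization is 2:1 and takes place during the clinic visit. On method the protocol says: "A block randomization scheme will be created before the study begins to ensure appropriate treatment allocation among the two groups". No stratification factor is named. If both eyes of a patient qualify, a rule applies instead: the worse eye gets laser and the fellow eye gets sham.
- **Entry (section 6).** Any eye with best corrected acuity of 20/32 or better on ETDRS testing, with no other acuity limit.
- **Primary outcome (section 8).** "Proportion of patients with vision loss to 20/40 or worse on ETDRS testing on two visits", with confirmation within 28 days. No minimum change from baseline is required.
- **Sample size (section 7).** "36 eyes will be enrolled based on power calculations for 80% power". The planned event rates are 40% or more in the sham arm and 15% in the laser arm. After citing a 40% rate of losing 5 or more letters among eyes at 20/25 or better, the section adds: "We assume a higher rate among eyes with 20/32 or better".

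**The concern.** Since 20/40 is the ETDRS line just below 20/32, an eye entering at 20/32 reaches the primary event with a loss of one line or less. An eye entering at 20/20 has to lose about three lines. Entry acuity is therefore very likely to be prognostic, and the protocol's own remark on the event rate points the same way. The value is also needed for eligibility, so it can be available before allocation.

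Blocks without strata control the number of eyes per arm but not the mix of starting acuities. With 12 eyes in the sham arm, a difference of two eyes changes that mix noticeably. An arm that by chance receives more 20/32 eyes will tend to show more failures, and a raw comparison of proportions would carry that along with any treatment effect.

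**Working it through.** **1. The plan's own figure.** Inputs from section 7: 40% versus 15%, 2:1, 80% power. Alpha is not stated; 0.05 two-sided is assumed. With pooled rate (0.40 + 2 × 0.15)/3 = 0.233:

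n(sham) = [1.960 × √(1.5 × 0.233 × 0.767) + 0.842 × √(0.40 × 0.60 + 0.15 × 0.85/2)]² / 0.25² = 35.005, rounded up to 36.

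This gives 36 sham + 72 laser = 108 eyes. As a total, 36 is not reproduced; with 12 + 24 eyes the power is about 39%. That is a separate matter. The steps below use 24:12 because that is what the protocol enrols, and they treat all 36 eyes as allocated from the list.

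**2. Size of the chance imbalance.** Let K of the 36 eyes be at 20/32 (share q = K/36, not given; one third to two thirds assumed), and let X of them fall among the 12 sham eyes (hypergeometric). The difference in share is D = X/12 − (K − X)/24. One eye moves D by 1/12 + 1/24 = 12.5 points, so 20 points or more means at least two sham eyes away from expectation.

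SD(D) = √[q(1 − q)(1/12 + 1/24) × 36/35]

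| Eyes at 20/32 | SD of D | Chance that D is 20 points or more, either way |
|---|---|---|
| 12 of 36 | 16.9 points | 26% |
| 18 of 36 | 17.9 points | 29% |
| 24 of 36 | 16.9 points | 26% |

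Simulated unstratified 2:1 blocks of 3 and 6, with shares of 30% and 50%, agree: SD 16-18 points, chance 25-29%.

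**3. Effect on the risk difference.** Shift = D × risk gap between 20/32 and better eyes, taking the same gap in both arms. The gap is not in the documents, so a range is shown for a one-SD imbalance (16.9 to 17.9 points).

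| Assumed gap | Shift | Share of the planned 25 points |
|---|---|---|
| 20 points | 3.4-3.6 points | about 14% |
| 30 points | 5.1-5.4 points | 20-22% |
| 40 points | 6.8-7.2 points | 27-29% |
| 50 points | 8.5-9.0 points | 34-36% |

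**4. If laser narrows the gap.** Take half the eyes at 20/32 and sham rates of 60% and 20% (average 40%). Scaled to the planned 15%, the laser rates are 22.5% and 7.5%, a gap of 15 points. Two thirds of D falls on the sham arm and one third on the laser arm, so a one-SD imbalance gives 17.9 × (2/3 × 0.40 + 1/3 × 0.15) = 5.7 points. That is 23% of 25, against 29% with a common gap.

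**5. Against the sampling error.** SE of the risk difference at the planned rates = √(0.40 × 0.60/12 + 0.15 × 0.85/24) = 15.9 points. The one-SD shift for a 40-point sham gap is (5.7/15.9)² = 13% to (7.2/15.9)² = 21% of that variance. It is a component of the sampling error, not an addition to it.

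**6. With stratified blocks.** In simulation, blocks of 3 or 6 within two acuity strata cut the SD of D to about 3.5-5 points. At a 40-point gap the one-SD shift becomes 3.5 × 0.40/25 = 6% to 5 × 0.40/25 = 8% of the planned effect.

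**7. Risk within the 20/32 line.** As an illustration, assume a stable eye, independent readings with SD 3 letters, 20/40 taken as 73 letters or fewer, and 9 follow-up visits each with a confirming test. With p = Φ((73.5 − true)/3), the chance of a confirmed event is 1 − (1 − p²)⁹: 85%, 59%, 31%, 13% and 4% at 74 to 78 letters, and 1% at 79. At 75 letters it is 38% with SD 2 and 70% with SD 4. The levels depend heavily on the assumptions. The pattern shows that letters carry information that a two-level split loses.

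**The case against.** The strongest reply is that nothing here is stated wrongly. The block scheme is still to be created, stratification factors can sit in a randomization plan, and adjustment for baseline acuity may be in the unseen SAP. This stands in part: no inference should be drawn about the SAP. But the list is fixed before the first patient, so an SAP cannot add strata afterwards. At the planned rates there would be only about 5 sham events (12 × 0.40) and 4 laser events (24 × 0.15), which makes adjustment alone fragile.

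A reader might go further and infer that chance imbalance distorts the result by about a third of the planned effect. The documents do not support that figure. It needs, for example, a 20-point imbalance and a 40-point gap in both arms (0.20 × 40 = 8 points; 8/25 = 32%). The gap is not given, and at gaps of 20-30 points a one-SD shift is only 14-22%. Nor do the documents call acuity the dominant predictor. Section 7 gives a direction only, and its remark follows a sentence about a 5-letter loss rather than about reaching 20/40.

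A reader might also infer bias or an inflated type I error. Neither follows. The shift averages zero over randomizations and already lies inside the sampling error.

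Three practical objections stand and shape the remedy:

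- Fixed 2:1 blocks of 3 leave 4 of 9 allocations predictable to anyone who knows the earlier ones (two if sham comes first in the block, one if second, one if third; three positions each). This is a single site where the laser operator knows the treatment given.
- Risk varies within the 20/32 line, so two strata do not balance all of it.
- Eyes of patients with both eyes eligible bypass the list.

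**Conclusion.** The point holds as a design weakness worth correcting. The protocol pairs a fixed endpoint one line below the entry limit with a small sham arm and an unstratified list, while itself expecting entry acuity to matter. The imbalance figures (26-29% chance of 20 points or more, SD 17-18 points) rest on the 24:12 split and an assumed 20/32 share of one third to two thirds. The effect on the result, 14% to 36% of the planned difference for a one-SD imbalance, rests further on an assumed risk gap of 20 to 50 points common to both arms, and is smaller if laser narrows that gap. What is at stake is precision, and the credibility of the one comparison actually realised if it is left unadjusted. The test remains valid. Neither the sample-size shortfall nor the worse-eye rule is cured by stratifying. If worse refers to acuity, which section 9 does not define, that rule would create a systematic imbalance of its own.

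**What to change.** - In section 9, prepare the 2:1 list in two strata by baseline ETDRS acuity: 20/32, and 20/25 or better. Use concealed block sizes that vary at random, for example 3 and 6.
- State that the acuity used for stratification is measured before allocation. Section 6 needs it for eligibility, but section 9 lists the acuity examination after randomization.
- Carry the stratum or, preferably, baseline letters into the primary comparison.
- Say how patients with both eyes eligible are allocated and analysed, since the stratified list does not reach them.

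The cost is a second list and one term in the analysis. Incomplete blocks may leave the arms one or two eyes away from 24:12.

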#### **Inclusion Criteria:**

1. Age  $\geq$ 18 years
2. Type 1 or type 2 diabetes mellitus
3. Clinical evidence of center-involved DME confirmed on OCT, and defined by OCT Central Subfield (CSF) thickness at the time of randomization by the following:
  - a. Zeiss Cirrus: 275 $\mu$  in women, and 290 $\mu$  in men
  - b. Heidelberg Spectralis: 290 $\mu$  in women, and 305 $\mu$  in men
4. Best corrected visual acuity of 20/32 or better on ETDRS testing

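### When both eyes qualify, the worse eye goes to laser and the fellow eye to sham by rule, so these eyes are not randomised and their arm depends on baseline status

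*Protocol*

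**What the plan says.** Protocol section 9 (Procedures Involved) presents a randomised comparison of subthreshold micropulse laser (SML) with sham. On the method it says: "A block randomization scheme will be created before the study begins to ensure appropriate treatment allocation among the two groups". On the unit it says: "At the time of randomization, only one eye will be randomized to either the treatment or observation". The next sentence covers patients with two eligible eyes: "one eye (worse eye) will be assigned to the treatment group and the fellow eye to the sham treatment group".

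Other sections that bear on this:

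- **Section 7 (Study Timelines)** sizes the trial at 36 eyes, "using a 2:1 ratio for randomization", and "assuming at least 40% of eyes monitored by observation alone will experience vision loss to 20/40 or worse", against 15% with SML.
- **Section 6 (Inclusion Criteria)** sets both an OCT central subfield thickness threshold and an acuity criterion: "Best corrected visual acuity of 20/32 or better on ETDRS testing". Neither is named as the measure of 'worse'.
- **Section 8 (Study Endpoints)** uses a fixed threshold for both primary outcomes: the proportion of patients reaching 20/40 or worse, and "Mean time to vision loss to 20/40 or worse on ETDRS testing on two visits" (no more than 28 days apart).
- **Section 9** ends: "All data will be analyzed in accordance to the" intention-to-treat principle. Nothing sets the eyes of bilateral patients apart.

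**The concern.** For a bilateral patient, anyone who knows which eye is worse knows each eye's arm before enrolment. Chance plays no part, so the usual justification for comparing the arms does not apply to these eyes.

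The allocation is also tied to prognosis. The primary outcomes ask whether and when an eye crosses 20/40. If 'worse' means lower acuity, SML eyes start nearer that line and will cross it more often and sooner even if the laser does nothing. On mean acuity change the effect is reversed: an eye picked because it measured lower tends to drift back up on retest, which flatters SML. If 'worse' means thicker on OCT, the same retest effect flatters SML on change in macular thickness. One rule can therefore push different outcomes in opposite directions, depending on a word the Protocol leaves open.

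**Working it through.** **1. Can the text be read as randomising bilateral eyes?** One might suppose that one eye is drawn at random and its fellow takes the other arm. The parenthesis in "one eye (worse eye) will be assigned to the treatment group and the fellow eye to the sham treatment group" rules this out because it names the eye that goes to SML. The sentence also sits badly with "At the time of randomization, only one eye will be randomized to either the treatment or observation", since two eyes enter and neither is randomised.

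**2. Allocation counts.** The plan's own figure is 36 eyes at 2:1, which is 24:12. The Protocol does not give the number of bilateral patients, k; I assume 3, 6 or 9. Single eyes number 36 − 2k and split 2:1; each bilateral patient adds one eye to each arm:

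SML = (36 − 2k) × 2/3 + k; sham = (36 − 2k)/3 + k.

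| k | SML : sham | Share of all eyes placed by rule | Share of sham eyes placed by rule |
|---|---|---|---|
| 0 | 24 : 12 | 0% | 0% |
| 3 | 23 : 13 | 6/36 = 17% | 3/13 = 23% |
| 6 | 22 : 14 | 12/36 = 33% | 6/14 = 43% |
| 9 | 21 : 15 | 18/36 = 50% | 9/15 = 60% |

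**3. Does the changed ratio matter for precision?** With 40% failure in both arms and eyes treated as independent, SE = √[0.40 × 0.60 × (1/SML + 1/sham)]. This gives 17.3 points at 24:12, then 17.0, 16.7 and 16.6 points for k = 3, 6 and 9. The ratio contradicts section 7, but precision is hardly affected.

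**4. From a within-pair gap to the whole trial.** Let the worse eye fail d more often than its fellow with no treatment effect, centred on the rate of the other eyes. The expected SML minus sham difference is then d × ½(k/SML + k/sham). The multiplier is 0.18, 0.35 and 0.51 for k = 3, 6 and 9. For k = 6: ½(6/22 + 6/14) = 0.35.

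**5. How large might d be?** The Protocol gives no distribution of baseline acuity, no retest error and no correlation between eyes, so this step is entirely assumed. The simulation took 'worse' as lower acuity, no treatment effect and mean drift set so that 40% of eyes fail. Base inputs were baseline 80 letters with SD 5, retest SD 2.5, both eyes measured at 74 letters or better, failure as two readings of 73 or fewer, inter-eye correlation 0.3 to 0.7, and drift SD 6 to 8 letters.

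- Failure at month 24: the worse eye fails about 9 to 18 points more often. If failure may be confirmed at any visit, the gap is about 10 to 20 points.
- With baseline SD 3.5, correlation 0.7 and drift SD 8, the gap falls to about 5 points.
- Spurious acuity gain for SML: about 1.3 to 1.8 letters within pairs, about 0.5 to 0.9 if retest SD is 1.5, and about 2 with the smaller baseline SD.

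A fair summary within pairs is 5 to 20 points of excess failure and 0.5 to 2 letters of spurious gain.

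**6. Over all 36 eyes with k = 6.** Failure: 0.35 × 5 = 1.8 and 0.35 × 20 = 7.0 points against SML. Acuity change: 0.35 × 0.5 = 0.2 and 0.35 × 2 = 0.7 letters in favour of SML. With d = 10, a true 25-point benefit would appear as 25 − 3.5 = 21.5 points.

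**7. Does baseline adjustment remove it?** Under the base inputs, comparing eyes with the same own baseline letter reverses the failure gap, to about 2 to 7 points in favour of SML within pairs. Adding the fellow eye's baseline to a probit model leaves between −0.4 and +0.3 points, and at most 0.1 letter on acuity change.

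**The case against.** Several points on the other side are sound.

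- **Adjustment can help.** If 'worse' is defined by acuity, the rule is a known function of both eyes' measured baselines, and modelling both can remove nearly all the bias. A reader might infer from the sign reversal that no adjustment works; that goes too far. But the remedy needs a definition the Protocol lacks, relies on the model being right, would be imprecise with 36 eyes, and does not make the eyes randomised.
- **The crude primary bias runs against SML.** A reader might infer that the rule could manufacture a positive primary result. On the crude comparison with 'worse' as lower acuity, it would not. The favourable bias is on mean acuity change, or on the primary outcome after adjustment for own baseline only.
- **The size is modest and unknown.** At trial level it is below the sampling standard error, and the number of bilateral patients is not given. This stands. Still, a confidence interval reflects sampling error and makes no allowance for bias in allocation.
- **The 1:1 entry is not a second harm.** A reader might infer lost power; step 3 shows otherwise. It is an inconsistency to correct.
- **The safety look.** Section 12 triggers a review once 12-month data exist for at least 10 eyes randomised to each group. A reader might infer that rule-assigned eyes are counted there. The text does not mention them and, read literally, could exclude them. It is unclear either way.
- **The SAP may deal with paired eyes.** Correlation and stratification commonly belong there, and their absence here is no fault. Allocation, however, is fixed in the Protocol, and an analysis plan cannot supply randomisation afterwards.

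**Conclusion.** The point stands and should be fixed. For every bilateral patient, section 9 replaces randomisation with a rule based on baseline status and does not define the rule's key word. Nothing in the Protocol keeps those eyes out of the comparison. That conclusion comes from the text alone and needs no assumed figures.

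The size of the bias does not come from the text. With 6 bilateral patients, 40% failure and 'worse' meaning lower acuity, the assumed inputs give roughly 2 to 7 points against SML on the primary proportion and under 1 letter in its favour on mean acuity change. The planned effect is 25 points and the standard error of the failure difference about 17 points. The documents do not support saying that the bias would dominate the result. The case for change is that part of a trial described as randomised would not be, in a way that is easily avoided.

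**What to change.** **Preferred.** Delete the worse-eye rule from section 9. For patients with two eligible eyes, use a separate pre-generated list to randomise which eye receives SML and which sham. Restate the expected overall ratio in section 7 (for example 22:14 with 6 bilateral patients), and say whether these eyes count towards the section 12 review. Analyse with bilateral status as a stratum and the pairing accounted for; the detail can sit in the SAP.

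The stratum is needed because bilateral eyes would still form 6/22 = 27% of SML eyes but 6/14 = 43% of sham eyes. If they failed 10 points more often (assumed), a crude comparison would shift by 10 × (0.273 − 0.429) = −1.6 points, in favour of SML; the stratified one would not.

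Cost: a short amendment, one extra list and one stratification term, with no extra patients or visits. Some worse eyes will receive sham.

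**Alternative.** Choose one study eye per patient at random and randomise it 2:1. This keeps the planned ratio and avoids correlated eyes, but needs one more patient for each bilateral patient to reach 36 eyes (3, 6 or 9 more in the cases above), each with at least 10 visits.
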